8.1.3 Baseline Period: Visit 2 (Week 0) (Randomization)

At the beginning of this visit, the investigator should assess the partial-onset seizure frequency over the 8-week Baseline Period as recorded in the subject diary. On the basis of the diary, the subject must have reported at least 2 partial-onset seizures per 28 days on average, with no more than 21 consecutive seizure-free days during the 8 weeks prior to entry into the Baseline Period. During this study, subjects must have reported at least 2 partial-onset seizures during the 8-week prospective Baseline Period to be eligible for randomization at Visit 2. If the subject is eligible to continue in the study, the following assessments will be performed:

- Concomitant medications

- Concomitant AEDs
- VNS assessments (for subjects with an implanted VNS device)
- Physical examination (complete)
- Vital signs (BP and pulse rate, including orthostatic assessments)
- Body weight assessment
- Height assessment
- Neurological examination (complete)
- 12-lead ECG (2 interpretable recordings [20 to 30 minutes apart] to be performed prior to any blood draws and vital signs assessment and, if possible, with the subject in the supine position for approximately 5 minutes preceding the recordings and during the recordings)
- Blood sample for clinical chemistry and hematology
- Blood sample for endocrinology
- Urine sample for urinalysis (for subjects ≥ 5 years of age)
- Urine pregnancy test (for females of childbearing potential)
- C-SSRS (for subjects ≥ 6 years of age)
- Achenbach CBCL
- BRIEF-P/BRIEF score
- PedsQL score
- Contact IXRS
- Randomization
- Dispense study medication
- Reminder to complete subject diary on a daily basis
- Review withdrawal criteria
- AE reporting
- Health care resource use

The subject will take the first dose of study medication in the clinic. The subject will be scheduled to return to the clinic as specified in [Table 5-1](#). On the morning of the next clinic visit, the subject should take concomitant AEDs and study medication at the usual time(s).

8.2 Titration Period: Week 1 to Week 6

Both clinic visits and telephone contacts will be conducted during the Titration Period, beginning with Telephone Contact 2 at the end of Week 1 and continuing through Visit 5 at the end of Week 6. The subject should take concomitant AEDs and study medication at the usual time(s) on the morning of each clinic visit.

At each clinic visit and telephone contact, the investigator, in conjunction with the subject and/or parent(s)/legal representative(s), will decide how to proceed with study medication dosing based on tolerability (including vital signs, body weight, 12-lead ECG, and AE reporting, as applicable to the type of contact). If the withdrawal of study medication is required during the Titration Period, the subject will enter the blinded Taper Period (Section 8.5).

8.2.1 Titration Period: Telephone Contact 2 (Week 1), Telephone Contact 3 (Week 3), and Telephone Contact 4 (Week 5)

During the Titration Period telephone contacts (Telephone Contact 2, Telephone Contact 3, and Telephone Contact 4), the following assessments will be performed:

- Concomitant medications
- Concomitant AEDs
- Reminder to complete subject diary on a daily basis
- Review withdrawal criteria
- AE reporting

8.2.2 Titration Period: Visit 3 (Week 2), Visit 4 (Week 4), and Visit 5 (Week 6)

During the Titration Period clinic visits (Visit 3, Visit 4, and Visit 5), the following assessments will be performed:

- Concomitant medications
- Concomitant AEDs
- VNS assessment (for subjects with an implanted VNS device)
- Physical examination (brief)
- Vital signs (BP and pulse rate, including orthostatic assessments)
- Body weight assessment
- Neurological examination (brief)
- 12-lead ECG (2 interpretable recordings [20 to 30 minutes apart] to be performed prior to any blood draws and vital signs assessment and, if possible, with the subject in the supine position for approximately 5 minutes preceding the recordings and during the recordings)
- Blood sample for clinical chemistry and hematology (Visit 4 and Visit 5 only)
- Urine sample for urinalysis (for subjects ≥ 5 years of age) (Visit 4 and Visit 5 only)
- Serum pregnancy test (for females of childbearing potential) (Visit 4 and Visit 5 only)
- Urine pregnancy test (for females of childbearing potential) (Visit 3 only)
- Blood sample for determination of concomitant AED plasma concentration (Visit 5 only)

- Blood sample for determination of LCM plasma concentration (Visit 5 only)
- C-SSRS (for subjects ≥ 6 years of age)
- Achenbach CBCL (same version used at Visit 2) (Visit 5 only)
- Contact IXRS
- Dispense study medication
- Study medication return
- Reminder to complete subject diary on a daily basis
- Review withdrawal criteria
- AE reporting
- Health care resource use

The subject will be scheduled to return to the clinic as specified in [Table 5-1](#). The morning of the next clinic visit, the subject should take concomitant AEDs and study medication at the usual time(s).

8.3 Maintenance Period: Week 7 to Week 16

Subjects who complete the Titration Period will enter the 10-week Maintenance Period at the study medication dose they received on the final day of the Titration Period. Dose reduction is not allowed during the Maintenance Period; subjects who require dose reduction during the Maintenance Period will be withdrawn from the study. Subjects who are withdrawn will enter the Taper Period (see Section [7.2.4](#)).

Beginning with Visit 6 at the end of Week 8 and continuing up to Visit 8 at the end of Week 16, alternating telephone contacts and clinic visits will be conducted during the Maintenance Period. The subject should take concomitant AEDs and study medication at the usual time(s) on the morning of each clinic visit.

8.3.1 Maintenance Period: Visit 6 (Week 8) and Visit 7 (Week 12)

During Visit 6 and Visit 7 (clinic visits) of the Maintenance Period, the following assessments will be performed:

- Concomitant medications
- Concomitant AEDs
- VNS assessments (for subjects with an implanted VNS device)
- Physical examination (brief)
- Vital signs (BP and pulse rate; including orthostatic assessments)
- Body weight assessment
- Neurological examination (brief)

- 12-lead ECG (2 interpretable recordings [20 to 30 minutes apart] to be performed prior to any blood draws and vital signs assessment and, if possible, with the subject in the supine position for approximately 5 minutes preceding the recordings and during the recordings)
- Blood sample for clinical chemistry and hematology (Visit 7 only)
- Urine sample for urinalysis (for subjects ≥ 5 years of age) (Visit 7 only)
- Serum pregnancy test (for females of childbearing potential) (Visit 7 only)
- Urine pregnancy test (for females of childbearing potential) (Visit 6 only)
- C-SSRS (for subjects ≥ 6 years of age)
- Contact IXRS
- Dispense study medication
- Study medication return
- Reminder to complete subject diary on a daily basis
- Review withdrawal criteria
- AE reporting
- Health care resource use

The subject will be scheduled to return to the clinic as specified in [Table 5-1](#). The morning of the next clinic visit, the subject should take concomitant AEDs and study medication at the usual time(s).

8.3.2 Maintenance Period: Telephone Contact 5 (Week 10) and Telephone Contact 6 (Week 14)

During the Maintenance Period telephone contacts (Telephone Contact 5 and Telephone Contact 6); the following assessments will be performed:

- Concomitant medications
- Concomitant AEDs
- Reminder to complete subject diary on a daily basis
- Review withdrawal criteria
- AE reporting

8.3.3 End of Maintenance Period: Visit 8 (Week 16)

For subjects who complete the Maintenance Period, Visit 8 will be the final Maintenance Period clinic visit.

At the completion of the Maintenance Period, investigators should discuss treatment options with the subject and/or their parent/legal representative to best manage the subject's epilepsy. Subjects who have completed the 10-week Maintenance Period will be given the opportunity to enroll in an open-label extension LCM study (EP0034). The decision made by the subject

or parent(s)/legal representative(s) and investigator regarding participation in the open-label extension study will be recorded in the IXRS and in the CRF. Subjects who plan to enroll in the open-label extension study will enter a 4-week blinded Transition Period.

Subjects who choose not to participate in the open-label extension study (EP0034) will enter a blinded Taper Period (2 to 4 weeks, depending on dose level achieved) (see Section 8.5) after completing Visit 8. Taper of LCM may not be required for some subjects who complete the Maintenance Period depending on the treatment option selected by the investigator in consultation with the subject and/or parent/legal guardian. These subjects should complete Visit 8 and then complete the 30-day Safety Follow-Up Period after Visit 8 (see Section 8.6); the Taper Visit is not required for subjects who complete the Maintenance Period and who do not undergo taper of LCM.

During Visit 8, the following assessments will be performed:

- Concomitant medications
- Concomitant AEDs
- VNS assessment (for subjects with an implanted VNS device)
- Physical examination (complete)
- Tanner Stage assessment
- Vital signs (BP and pulse rate, including orthostatic assessments)
- Body weight assessment
- Height assessment
- Head circumference
- Neurological examination (complete)
- 12-lead ECG (2 interpretable recordings [20 to 30 minutes apart] to be performed prior to any blood draws and vital signs assessment and, if possible, with the subject in the supine position for approximately 5 minutes preceding the recordings and during the recordings)
- Blood sample for clinical chemistry and hematology
- Blood sample for endocrinology
- Urine sample for urinalysis (for subjects ≥ 5 years of age)
- Serum pregnancy test (for females of childbearing potential)
- Blood sample for measurement of concomitant AED plasma concentrations
- Blood sample for measurement of LCM plasma concentration
- C-SSRS (for subjects ≥ 6 years of age)
- Clinical Global Impression of Change
- Caregiver's Global Impression of Change

- Achenbach CBCL (same version used at Visit 2)
- BRIEF-P/BRIEF score (same version used at Visit 2)
- PedsQL score (same version used at Visit 2)
- Contact IXRS
- Dispense study medication for the following 4-week Transition Period or Taper Period (2 to 4 weeks), as applicable
- Study medication return
- Reminder to complete subject diary on a daily basis
- Review withdrawal criteria
- AE reporting
- Health care resource use

Subjects who plan to enroll in EP0034, will be scheduled to return to the clinic as specified in [Table 5-2](#) and subjects who do not plan to enroll in EP0034 will be scheduled to return to the clinic as specified in [Table 5-3](#). Subjects who do not plan to enter either the Transition Period or the Taper Period due to other treatment choices, should be scheduled to return for a Safety Follow-Up Visit as specified in [Table 5-3](#). The morning of the next clinic visit, the subject should take concomitant AEDs and study medication at the usual time(s).

8.4 Transition Period

Subjects who complete the Maintenance Period and plan to participate in EP0034 will enter a blinded Transition Period of 4 weeks.

8.4.1 Transition Period: Transition Visit 1 (Week 17), Transition Visit 2 (Week 18), and Transition Visit 3 (Week 19)

During Transition Visit 1, Transition Visit 2, and Transition Visit 3 (clinic visits), the following assessments will be performed:

- Concomitant medications
- Concomitant AEDs
- VNS assessments (for subjects with an implanted VNS device)
- Physical examination (brief)
- Vital signs (BP and pulse rate; including orthostatic assessments)
- Body weight assessment
- Neurological examination (brief)
- C-SSRS (for subjects ≥ 6 years of age)
- Contact IXRS
- Dispense study medication

- Study medication return
- Reminder to complete subject diary on a daily basis
- Review withdrawal criteria
- AE reporting
- Health care resource use

8.4.2 Transition Period: Transition Visit 4 (Week 20)

During Transition Visit 4 (clinic visit), the following assessments will be performed:

- Concomitant medications
- Concomitant AEDs
- VNS assessment (for subjects with an implanted VNS device)
- Physical examination (complete)
- Vital signs (BP and pulse rate, including orthostatic assessments)
- Body weight assessment
- Neurological examination (complete)
- 12-lead ECG (2 interpretable recordings [20 to 30 minutes apart] to be performed prior to any blood draws and vital signs assessment and, if possible, with the subject in the supine position for approximately 5 minutes preceding the recordings and during the recordings)
- Blood sample for clinical chemistry and hematology
- Urine sample for urinalysis (for subjects ≥ 5 years of age)
- Urine pregnancy test (for females of childbearing potential)
- Blood sample for measurement of concomitant AED plasma concentrations
- Blood sample for measurement of LCM plasma concentration
- C-SSRS (for subjects ≥ 6 years of age)
- Contact DXRS
- Study medication return
- Subject diary return
- Review withdrawal criteria
- AE reporting
- Health care resource use

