Subjects who achieved at least the minimum target study medication (LCM or matching placebo) dose for the final 3 days of the Titration Period will enter a 10-week Maintenance Period on the study medication dose achieved on the final day of the Titration Period. Lacosamide dose (or matching placebo) will remain stable throughout the Maintenance Period. Subjects who complete the Maintenance Period and plan to participate in the open-label extension study (EP0034) will enter the blinded Transition Period. Subjects who require a change in dose during the Maintenance Period will be withdrawn and enter the

blinded Taper Period. Subjects who choose not to participate in EP0034 will also enter the Taper Period.

Transition Period

Subjects who complete the Maintenance Period and plan to participate in the open-label extension study (EP0034) will enter a 4-week blinded Transition Period. Subjects randomized to LCM will maintain their Maintenance Period dose during the Transition Period. Subjects randomized to placebo will transition to LCM in a double-blind fashion in accordance with the schedule provided in [Table 7-4](#).

Taper Period

The blinded Taper Period (2 to 4 weeks, depending on dose level achieved) is for subjects who will not be entering the open-label extension study (EP0034) for any of the following reasons:

- Subject does not complete the Titration Period, the Maintenance Period, or the Transition Period.
- Subject does not choose to enroll in the open-label extension study (EP0034) after completing the Maintenance Period or the Transition Period.

Taper of LCM may not be required for some subjects who discontinue study medication prematurely, depending on the treatment option selected by the investigator in consultation with the subject and/or parent/legal representative.

The dosing of study medication for the Taper Period is provided in [Table 7-5](#).

Safety Follow-Up Period

There will be a 30-day Safety Follow-Up Period for subjects not entering the open-label extension study (EP0034).

Unscheduled visits can be conducted at the discretion of the investigator.

Detailed schedules of study procedures are provided in [Section 5.2](#), and study schematic diagrams are included in [Section 5.3](#).

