5.1.1 Study duration per subject

Each subject's participation in the study begins with an 8-week Baseline Period. Each subject's total duration of study medication administration is up to 24 weeks; this includes a 6-week Titration Period, a 10-week Maintenance Period, and a 4-week Transition Period (for subjects who plan to enter the open-label extension study [EP0034]) and a Taper Period (2 to 4 weeks, depending on dose level achieved for subjects who will not be entering EP0034). The total study duration can be up to 36 weeks, including the 30-day Safety Follow-Up Period. Both the total duration of study medication and the total study duration include the possibility of a subject who completes the Transition Period choosing not to participate in EP0034 and having to enter the Taper Period.

The end of the study is defined as the date of the last visit of the last subject in the study.

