- ⁿ The BRIEF-P should be used for subjects who are ≥ 2 years to < 5 years of age at Visit 2, and the BRIEF should be used for subjects who are ≥ 5 years of age at Visit 2. The same version of the scale that was completed at Visit 2 (BRIEF-P or BRIEF) should be maintained for each subject for the duration of the study. The BRIEF-P and BRIEF will be used only in countries where a translated version is available.
- ^o The version of the PedsQL used at Visit 2 should be consistent with the subject's age at Visit 2 and should be maintained for each subject for the duration of the study. The PedsQL will be used only in countries where a translated version is available.
- ^p At the end of Visit 2, subjects should take the first dose of study medication in the clinic.
- ^q The subject diary will be dispensed at Visit 1. At all subsequent visits, the subject and/or legal representative(s) will be reminded to complete the diary on a daily basis.

Table 5-2 Schedule of study assessments (Transition Period)

Assessment	Transition Period (4 weeks) ^a			
	TV1	TV2	TV3	TV4
Visit				
Week in study	17 ^a	18	19	20
Concomitant medications	X	X	X	X
Concomitant AEDs	X	X	X	X
VNS assessments ^b	X	X	X	X
Physical examination (complete)				X
Physical examination (brief)	X	X	X	
Vital signs (BP and pulse rate, including orthostatic assessment)	X	X	X	X
Body weight	X	X	X	X
Neurological examination (complete)				X
Neurological examination (brief)	X	X	X	
12-lead ECG ^c				X
Clinical chemistry/hematology				X
Urinalysis ^d				X
Urine pregnancy test ^e				X
Concomitant AED plasma ^f concentrations				X
LCM plasma concentration ^f				X
C-SSRS ^g	X	X	X	X
Contact IXRS	X	X	X	X
Dispense study medication	X	X	X	
Study medication return	X	X	X	X
Subject diary ^h	X	X	X	X
Withdrawal criteria	X	X	X	X
AE reporting	X	X	X	X
Health care resource use	X	X	X	X

AE=adverse event; AED=antiepileptic drug; BP=blood pressure; C-SSRS=Columbia-Suicide Severity Rating Scale; ECG=electrocardiogram; IXRS=interactive voice/web response system; LCM=lacosamide; TV=Transition Visit; VNS=vagus nerve stimulation

Note: For all visits shown in Table 5-2, a window of ± 2 days relative to Visit 2 (Baseline Period) is applicable. Each visit should occur at the end of the week indicated in accordance with this time window.

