^a At the end of Visit 8, (Maintenance Period), subjects may be eligible to participate in an open-label extension study (EP0034). Subjects who plan to enroll in the open-label extension study will enter a 4-week blinded Transition Period.

^b Only applicable for subjects with an implanted VNS device.

^c A 12-lead ECG (2 interpretable recordings) will be performed prior to any blood draws and vital signs

Table 5-2 Schedule of study assessments (Transition Period)

Assessment	Transition Period (4 weeks) ^a			
	TV1	TV2	TV3	TV4
Visit				
Week in study	17 ^a	18	19	20

assessment. The subject should rest in the supine position for approximately 5 minutes before the ECG recording and during the recordings if possible. The recordings should be made 20 to 30 minutes apart.

^d Urinalysis will be performed for subjects ≥ 5 years of age only.

^e Pregnancy tests will be performed for female subjects of childbearing potential only.

^f Blood samples for analysis of concomitant AED plasma concentrations and/or LCM will be drawn along with clinical chemistry, hematology, and endocrinology samples, as applicable.

^g The C-SSRS will be completed for all subjects ≥ 6 years of age.

^h The subject diary will be returned at TV4. At all other visits, the subject and/or legal representative(s) will be reminded to complete the diary on a daily basis.

Table 5-3 Schedule of study assessments (Taper Period and Safety Follow-Up Period)

Assessment	Taper Period ^a (2 to 4 weeks)		Safety Follow-Up Period ^b (30 days)	
	TV ^c	Taper Visit ^d	Safety Follow-Up Visit	Safety Follow-Up Telephone Contact
Week in study	17	18, 19, or 20	20, 21, or 22	22, 23, or 24
Concomitant medications	X	X	X	X
Concomitant AEDs	X	X	X	X
VNS assessment ^e		X	X	
Physical examination (brief)		X		
Physical examination (complete)			X	
Vital signs (BP and pulse rate, including orthostatic assessment)		X	X	
Body weight		X	X	
Neurological examination (brief)		X		
Neurological examination (complete)			X	
ECG (12-lead) ^f		X	X ^g	
Clinical chemistry/hematology		X	X ^g	
Endocrinology		X	X ^g	
Urinalysis ^h		X	X	
Serum pregnancy test		X	X ⁱ	

Table 5-3 Schedule of study assessments (Taper Period and Safety Follow-Up Period)

Assessment	Taper Period ^a (2 to 4 weeks)		Safety Follow-Up Period ^b (30 days)	
	Visit	Taper Visit ^d	Safety Follow-Up Visit	Safety Follow-Up Telephone Contact
Week in study	T7 ^c	18, 19, or 20	20, 21, or 22	22, 23, or 24
Urine pregnancy test			X ⁱ	
C-SSRS ^j		X	X	
Contact IXRS		X		

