ⁱ Pregnancy tests will be performed for female subjects of childbearing potential only. A serum pregnancy test will be performed at the Safety Follow-Up Visit only if blood is collected for other laboratory tests. If no blood is collected for other assessments, then a urine pregnancy test will be performed.

^j The C-SSRS will be completed for all subjects ≥ 6 years of age.

Table 5-3 Schedule of study assessments (Taper Period and Safety Follow-Up Period)

	Taper Period ^a (2 to 4 weeks)		Safety Follow-Up Period ^b (30 days)	
Assessment				
Visit	T7 ^c	Taper Visit ^d	Safety Follow-Up Visit	Safety Follow-Up Telephone Contact
Week in study	17	18, 19, or 20	20, 21, or 22	22, 23, or 24

^x At T7, the subject and/or legal representative(s) will be reminded to complete the diary on a daily basis. The subject diary will be returned at the Taper Visit.

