8.8 Early Termination Visit

Subjects who withdraw from the study prematurely for any reason, including AEs, must complete an Early Termination Visit. At the time of withdrawal from the study, investigators should discuss treatment options with the subject and/or their parent/legal guardian to best manage the subject's epilepsy. Taper of LCM may not be required for some subjects who discontinue study medication prematurely, depending on the treatment option selected by the investigator in consultation with the subject and/or parent/legal guardian. These subjects should complete the Early Termination Visit and then complete the 30-day Safety Follow-Up Period.

The following assessments should be completed at the Early Termination Visit and prior to subjects entering the blinded Taper Period (2 to 4 weeks).

- Concomitant medications
- Concomitant AEDs
- Changes in VNS settings
- Physical examination (complete)
- Tanner Stage assessment
- Vital signs (BP and pulse rate, including orthostatic assessments)
- Body weight assessment
- Height assessment
- Head circumference
- Neurological examination (complete)
- 12-lead ECG (2 interpretable recordings to be performed prior to any blood draws and vital signs assessment and, if possible, with the subject in the supine position for approximately 5 minutes preceding the recordings and during the recordings)
- Blood sample for clinical chemistry and hematology
- Blood sample for endocrinology
- Urine sample for urinalysis (for subjects ≥ 5 years of age)
- Serum pregnancy test (for females of childbearing potential)
- Blood sample for measurement of concomitant AED plasma concentrations
- Blood sample for measurement of LCM plasma concentration
- C-SSRS (for subjects ≥ 6 years of age)
- Clinical Global Impression of Change
- Caregiver's Global Impression of Change
- Achenbach CBCL (same version used at Visit 2)
- BRIEF-P/BRIEF score (version consistent with that used at Visit 2)
- PedsQL score (version consistent with that used at Visit 2)
- Contact IXRS
- Dispense study medication for the Taper Period (2 to 4 weeks)
- Study medication return
- Reminder to complete subject diary on a daily basis
- AE reporting
- Health care resource use

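### A subject who completes Transition, declines EP0034 and tapers has no scheduled taper supply and no diary, because Transition Visit 4 takes both back and no other visit on that route issues them

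*Protocol*

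**What the plan says.** **The route.** Protocol section 5.1 lists the reasons for entering the Taper Period. One is: "Subject does not choose to enroll in the open-label extension study (EP0034) after completing the Maintenance Period or the Transition Period". Section 5.1.1 adds that the maximum durations "include the possibility of a subject who completes the Transition Period choosing not to participate in EP0034 and having to enter the Taper Period". SAP section 2.3 repeats the reason, and SAP section 3.2.2 allows the Taper Period to start after the last Transition dose.

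**Transition Visit 4 (TV4).** Table 5-2 marks the row "Dispense study medication" at TV1, TV2 and TV3 only. The TV4 list in section 8.4.2, introduced by "During Transition Visit 4 (clinic visit), the following assessments will be performed", includes return of study medication and of the diary and has no dispensing item. Footnote h of Table 5-2 says: "The subject diary will be returned at TV4".

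**The Taper Period.** Table 5-3 has no dispensing row, but it lists medication return at the Taper Visit and the diary at both the telephone contact (T7) and the Taper Visit. Its diary footnote says: "The subject diary will be returned at the Taper Visit". Sections 8.5.1 and 8.5.2 match the table.

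**The visits that do issue taper supply.** Visit 8 (section 8.3.3) dispenses for Transition or for Taper, as applicable. The Early Termination Visit (section 8.8) dispenses for Taper, and its population is defined thus: "Subjects who withdraw from the study prematurely for any reason, including AEs, must complete an Early Termination Visit".

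**The concern.** Two parts of the protocol give a site incompatible instructions for the same subject. One part sends a Transition completer who declines EP0034 into a stepwise taper. The other has the site collect all study medication and the diary at the visit immediately before that taper, and schedules nothing to replace them.

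What is at stake is mainly patient safety: a child could leave TV4 without the supply on which the protocol's own taper table depends. Both arms are affected, because by Week 20 placebo-randomised subjects have been moved to lacosamide (Table 7-4). A secondary consequence is that the daily seizure diary expected during Taper would not be in the subject's hands.

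**Working it through.** **1. Do the stated maxima count this route?** Period lengths from section 5.1.1: Baseline 8 weeks, Titration 6, Maintenance 10, Transition 4, Taper up to 4, Safety Follow-Up 30 days.

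- On medication, Transition then Taper: 6 + 10 + 4 + 4 = 24 weeks, as stated.
- On medication, Transition without Taper, or Taper without Transition: 6 + 10 + 4 = 20 weeks.
- Total, Transition then Taper: 8 + 24 + 30/7 = 36.3 weeks, against 36 stated.
- Total, Taper without Transition: 8 + 20 + 30/7 = 32.3 weeks.

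Only Transition followed by Taper reproduces both figures, so the route is planned.

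**2. Which scheduled contacts could supply this subject's taper?**

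- Visit 8: supplies Transition or Taper. This subject takes the Transition branch.
- TV1 to TV3: dispensing is listed, for the Transition Period, which ends at Week 20.
- TV4: medication return only. Section 7.7 also requires all used and unused containers to come back at each visit, so leftover supply does not fill the gap.
- T7 and Taper Visit: no dispensing.
- Early Termination Visit: dispenses taper supply, but is for premature withdrawal. Section 5.1 treats not completing Transition and completing it but declining EP0034 as separate reasons for Taper.
- Unscheduled Visit (section 8.7): dispensing is not among the required items.

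Visits that supply taper medication on this route: 0. Scheduled dispensing runs to Week 20 against a maximum of 24, a gap of up to 24 − 20 = 4 weeks.

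**3. Could the dose reached need no taper?** Doses at TV4 come from Tables 7-3 and 7-4; weekly taper steps come from Table 7-5.

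- Under 30 kg: 8 to 12 mg/kg/day (lacosamide arm) or 8 mg/kg/day (placebo arm): 4 steps.
- 30 to under 50 kg: 6 to 8 mg/kg/day (lacosamide arm) or 6 mg/kg/day (placebo arm): 3 or 4 steps.
- 50 kg and over: 300 to 400 mg/day (lacosamide arm) or 300 mg/day (placebo arm): 3 or 4 steps.

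None of these doses falls in a row that Table 7-5 marks as not requiring taper.

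**4. The diary.** It is issued at Visit 1 (Table 5-1 and section 8.1.1) and collected at TV4. T7 then calls for a reminder to complete it daily, and the Taper Visit collects it again. Stated re-issues after TV4: 0.

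**The case against.** The strongest reply is that taper is not compulsory for every such subject. The last sentence of section 8.5 excuses subjects who complete Maintenance and do not undergo taper. Every Transition subject has completed Maintenance, so on its plain words that sentence can reach them. This stands. A reader might infer from section 5.1.1 that all Transition completers who decline EP0034 must taper; read with section 8.5, the documents do not support that. The waiver does not close the gap, because it helps only those who do not taper.

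Second, the group is narrow. A subject who withdraws before TV4 has not completed Transition and can leave through the Early Termination Visit, which does dispense. This also stands: only decisions made at or after TV4 are uncovered.

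Third, a site would probably cope. TV4 includes an IXRS contact and a review of withdrawal criteria, and section 12.1 lets the investigator depart from the protocol to avert an immediate hazard. That makes the literal outcome less likely. But section 7.9 ties kit issue to the visit schedule, and that schedule has no dispensing at TV4.

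Fourth, a reader might infer that Taper adverse event data or efficacy results are compromised. The documents do not support either inference. Adverse event reporting is its own item at T7 and the Taper Visit, obtained by spontaneous report and prompting (section 11.1.2). The seizure-based efficacy variables end with Maintenance (sections 4.1.1 and 4.1.2), and imputation is not carried into Transition or Taper (section 13.6).

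Finally, timing is not a real problem. Footnotes c and d of Table 5-3 tie T7 and the Taper Visit to the Taper Period itself, and the table's note says its week numbers do not apply to other entry times.

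**Conclusion.** The contradiction is real and narrow. Sections 5.1 and 5.1.1 provide for Taper after a completed Transition Period. Table 5-2 and section 8.4.2, which agree with each other, remove medication and diary at TV4, and no scheduled visit on that route replaces them. For a Transition completer who decides at or after TV4 not to enter EP0034 and who does taper, the schedule leaves 3 or 4 weeks of Table 7-5 steps without supply and the same period without a diary.

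The number of subjects cannot be derived: the documents give no rate for declining EP0034 after Transition. The conclusion needs no such assumption. It rests on the schedule being followed as written and on at least one subject taking a route that the protocol itself counts in its maximum durations. The consequences are for supply, subject safety and Taper diary data. The primary and secondary efficacy analyses and adverse event collection are unaffected.

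**What to change.** The sponsor should confirm which taper rule applies to Transition completers who do not enter EP0034, and then make these places agree with it: sections 5.1, 5.1.1, 7.2.4, 8.4.2 and 8.5 (including 8.5.1 and 8.5.2), Table 5-2 with footnote h, Table 5-3 with its diary footnote, and the IXRS dispensing schedule.

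If Taper after Transition is confirmed, the TV4 dispensing and diary-return items need to be conditional on whether the subject is entering EP0034. If it is not, sections 5.1 and 5.1.1 and the 24-week and 36-week maxima need to change instead. This point proposes no dose, taper step or clinical rule.

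The cost is a few lines in a protocol amendment. If Taper after Transition is kept, an IXRS branch at TV4 is also needed. No new visit or procedure is required.
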